## **Treatment Procedures**

One of the investigators will obtain written informed consent for this study from all patients or their legal representative (LAR) prior to the performance of any protocol procedure. Should any patient who previously had surrogate consent provided by their LAR regain their capacity to provide consent on their own, we will collect consent directly from that patient. Per customary UCLA clinical practice, medical history will be taken, physical exam performed and labs drawn prior to transplant.

## DRUG THERAPY

### *Group 1*

#### Basiliximab

- Dose #1: 20mg IV within 2 hours of transplant
- Dose #2: 20mg IV Post-operative day #4

#### Tacrolimus (with basiliximab induction)

- Beginning day #5 post-transplant or when SCr  $\leq$  1.8 mg/dl (subjects off dialysis) to six months: 0.03-0.1mg/kg q12h PO to maintain whole blood trough concentration of 4-6ng/mL

#### Mycophenolate mofetil

- 500 mg po bid

#### Corticosteroids (SOC): Per UCLA protocol

#### Post-operative taper:

- Post-op day 1-      methylprednisolone 50mg IVP Q6H
- Post-op day 2-      methylprednisolone 40mg IVP Q6H
- Post-op day 3-      methylprednisolone 30mg IVP Q6H
- Post-op day 4-      methylprednisolone 20mg IVP Q6H
- Post-op day 5-      methylprednisolone 20mg IVP Q12H
- Post-op day 6-      methylprednisolone 10mg IVP Q12H  
until taking PO, then change to: prednisone 20mg PO QAM

### *Group 2*

#### Basiliximab

- Dose #1: 20mg IV within 2 hours of transplant

- Dose #2: 20mg IV Post-operative day #4

#### Tacrolimus (with basiliximab induction)

- Beginning day #5 post-transplant or when SCr  $\leq$  1.8 mg/dl (subjects off dialysis) to POD 30: 0.03-0.1mg/kg q12h PO to maintain whole blood trough concentration of 4-6ng/mL
- POD 31; reduce to tacrolimus to 2-5ng/mL in presence of everolimus levels 3-8 ng/mL

#### Mycophenolate mofetil

- 500 mg po bid up to POD 30: reduce mycophenolate mofetil following achievement of steady state everolimus (POD 35) as clinically indicated

#### Corticosteroids (SOC): Per UCLA protocol

##### Post-operative taper:

- Post-op day 1- methylprednisolone 50mg IVP Q6H
- Post-op day 2- methylprednisolone 40mg IVP Q6H
- Post-op day 3- methylprednisolone 30mg IVP Q6H
- Post-op day 4- methylprednisolone 20mg IVP Q6H
- Post-op day 5- methylprednisolone 20mg IVP Q12H
- Post-op day 6- methylprednisolone 10mg IVP Q12H until taking PO, then change to: prednisone 20mg PO QAM

#### Everolimus (delayed)

- Add by POD 30: 1 mg po bid and adjusted to maintain whole blood trough concentrations of 3-8 ng/ml.

##### *Group 3 (control):*

#### Tacrolimus (without basiliximab induction)

- Beginning day #1 post-transplant to six months: 0.03-0.1mg/kg q12h PO to maintain whole blood trough concentration of 5-12ng/mL
- Six months to one year: maintain whole blood trough concentration of 5-10ng/mL

#### Mycophenolate mofetil

- 500 mg po bid

Corticosteroids (SOC): Per UCLA protocol

Post-operative taper:

- Post-op day 1- methylprednisolone 50mg IVP Q6H
- Post-op day 2- methylprednisolone 40mg IVP Q6H
- Post-op day 3- methylprednisolone 30mg IVP Q6H
- Post-op day 4- methylprednisolone 20mg IVP Q6H
- Post-op day 5- methylprednisolone 20mg IVP Q12H
- Post-op day 6- methylprednisolone 10mg IVP Q12H  
until taking PO, then change to: prednisone 20mg PO QAM

**Calcineurin Inhibitor Rescue Therapy**

- If after 1 episode of acute rejection, full dose tacrolimus or cyclosporine may be used per UCLA liver transplant protocol.

**Infectious disease**

- Prophylaxis and treatment of all infectious diseases will be per UCLA liver transplant protocol

**Basiliximab Preparation and Administration**

The 20mg dose of basiliximab will be diluted in 50mL of sterile 0.9% sodium chloride and may be administered via central or peripheral line over 20 to 30 minutes.

Gently invert the bag to avoid foaming. Once the infusion is prepared, it should be administered IV within four hours. Basiliximab is stable for up to 24 hours at 2-8°C. Infusion of basiliximab must be permanently terminated if the patient develops signs or symptoms suggestive of a severe allergic reaction

**Acute Rejection Assessments and Procedures**

- All patients with an unexplained deterioration in liver function (changes in total bilirubin, aspartate aminotransferase, alanine aminotransferase, alkaline phosphatase, or  $\gamma$ -glutamyltransferase concentrations) or the appearance of clinical signs of rejection (fever, jaundice, pruritis, ascites, or hepatic tenderness) will receive a liver biopsy
- Treatment of acute rejection per standard clinical practice at UCLA

### **Definition of Rejection**

The pathology department will classify any liver acute rejection episode per routine UCLA protocol.

### **Evaluation of CD25 cell count**

- 5cc of blood will be drawn from the patient each day post-transplant until hospital discharge
- 5cc of blood will be drawn at each post-transplant clinic visit
- Monitoring of CD25 cell counts will take place over first 3 months post-transplant

### **Adverse Events**

An adverse event is any adverse change from the patient's pre-treatment condition, which occurs during the course of the clinical trial, whether considered related to the treatment or not. Clinical adverse event will be graded on a 3 point scale (mild, moderate, severe) by the following definitions

1. mild- discomfort noticed, but no disruption of normal daily activity
2. moderate- discomfort sufficient to decrease or affect normal daily activity
3. severe- incapacitating - inability to work or perform normal daily activity

Adverse events will be monitored in the hospital and at clinic visits.

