Clearly, the primary objective assesses rate and severity of rejection, allograft loss and death as well as post-operative renal function (measured as estimated GFR). The proposed study will also evaluate the mTOR class effects (e.g., dyslipidemia, impaired wound healing and proteinuria) and in addition, it will monitor closely the potential safety effects of chronic mTOR inhibitor therapy upon infectious complications such as CMV, and HBV and HCV.

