## Secondary Objectives

- Glomerular Filtration Rate (eGFR); Cockcroft and Gault (MDRD)
- To determine the incidence of confirmed acute rejection episodes in patients undergoing orthotopic liver transplant at 1, 3 and 6 months post-transplant
- To determine the tolerability and adverse event profile of basiliximab, delayed dose tacrolimus, mycophenolate mofetil, SOC corticosteroids and Everolimus during the first six months post-transplant
- To determine the incidence of infectious complications during the first six months post-transplant
- To determine the time to the first episode of acute rejection
- To determine the severity of each acute rejection episode
- To determine the incidence of death and/or graft failure within the first six months post-transplant
- To determine the number of patients requiring full dose CNI rescue therapy
- To determine the mean serum creatinine concentration and eGFR: Cockcroft and Gault (MDRD) at weeks 1, 2, 4, 8, 12, 16, 20 and 24 post OLT
- To monitor CD25 cell count for the first 3 months post-transplant
- Economic analysis to determine cost-effectiveness of induction therapy with IL-2 monoclonal antibody
- Economic analysis to determine cost-effectiveness of delayed therapy with everolimus

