## **Safety objectives**

To evaluate:

- All AE/SAEs with emphasis on viral infections and reactivation (CMV, EBV, HIV, Hepatitis B and Hepatitis C), hematological and metabolic laboratory parameters, gastrointestinal side effects and malignancies.
- Incidence of treatment-related side effects including incidence of new onset diabetes mellitus (NODM), serum/blood lipid panel, neurotoxicity and hypertension.
- Incidence and reason (e.g. AE) for premature discontinuation of study medication, and premature withdrawal from the study.
- Incidence and reason (e.g. AE) for dose interruption and dose adjustment of study medication.

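### The adverse event baseline is undefined for a drug started about day 30, laboratory toxicities have no severity grade, and the six-month window dilutes the everolimus safety contrast

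*Protocol*

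**What the plan says.** The protocol's Adverse Events section counts any adverse change from the patient's "pre-treatment condition, which occurs during the course of the clinical trial", related to treatment or not. It does not date the pre-treatment condition. Severity follows one rule: "Clinical adverse event will be graded on a 3 point scale (mild, moderate, severe) by the following definitions". The lowest grade reads "mild- discomfort noticed, but no disruption of normal daily activity" and the highest "severe- incapacitating - inability to work or perform normal daily activity". Neither document gives a laboratory threshold or a laboratory toxicity scale.

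The safety aims rest largely on laboratory findings. The Introduction says that the study will "evaluate the mTOR class effects (e.g., dyslipidemia, impaired wound healing and proteinuria". The Safety objectives list, within the aim covering all adverse events, "hematological and metabolic laboratory parameters, gastrointestinal side effects and malignancies", and separately name new-onset diabetes and the lipid panel. The Everolimus dosing section names falls in platelets, hemoglobin and white cells, and rises in lipids, as reasons for dose adjustment.

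On the window, the tolerability aim under Secondary Objectives covers the combined regimen, ending "SOC corticosteroids and Everolimus during the first six months post-transplant". In the Drug Therapy lists, Groups 1 and 2 have the same regimen until everolimus is added to Group 2 about one month after transplant. The protocol's Statistical analysis section is still to be written. The SAP names tests but no safety baseline, window or laboratory summary.

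**The concern.** Comparing Group 2 with Group 1 is the only contrast that isolates delayed everolimus with its accompanying tacrolimus and mycophenolate changes. Three gaps in the safety definitions weaken it.

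- **Reference.** The baseline is undated in a trial where one investigational drug starts about a month, and a new liver, after the others.
- **Grading.** The severity scale records symptoms and function. Cytopenia, dyslipidemia and proteinuria can be silent, so the effects of most interest may carry no grade.
- **Window.** Six-month incidence mixes a month of identical treatment with the months in which the arms differ.

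At stake is whether the trial can report the frequency and severity of everolimus toxicity on a basis common to the arms. The trial is open label, so a wholly subjective grade is also assigned by someone who may know the arm.

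**Working it through.** The documents give no safety event rates, safety power or laboratory trajectories, so there is no stated figure to reproduce. The 2:2:1 allocation of 90 does agree with itself: 90 × 2/5 = 36, 36, and 90 × 1/5 = 18.

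**Reference point: two readings**

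1. *Before transplant.* Basiliximab is given within 2 hours of transplant in Groups 1 and 2, and control tacrolimus starts on day 1, so this is the natural reading. As an illustration with assumed values, take platelets of 60 before transplant, 200 at POD 30 and 80 on everolimus. The fall is (200 - 80)/200 = 60%, yet 80 is better than 60, so there is no adverse change from the pre-transplant condition.
2. *Before everolimus.* The Investigational Treatment section calls the first everolimus dose Day 1 of the treatment period. Under the Drug Therapy lists only Group 2 receives everolimus. Group 2 would then be judged from about POD 30, and Groups 1 and 3 from before transplant.

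The first reading can miss a deterioration; the second compares arms on different baselines. Neither gives one reference suited to the everolimus period in all arms.

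**Grading**

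All three grades are anchored in discomfort or activity, and the scale is stated for clinical events. A silent laboratory abnormality therefore has no grade.

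**Window**

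Let p1 be the proportion with a first event by POD 30, equal in expectation in Groups 1 and 2 because they are treated alike until then. Let q be the later risk. Then:

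six-month incidence = p1 + (1 - p1) × q

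difference between arms = (1 - p1) × (q2 - q1)

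This assumes that q is the same in patients with and without an early event. With assumed q of 20% (Group 1) and 40% (Group 2):

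| p1 | Group 1 | Group 2 | Difference |
|---|---|---|---|
| 0% | 20% | 40% | 20 points |
| 30% | 0.30 + 0.70 × 0.20 = 44% | 0.30 + 0.70 × 0.40 = 58% | 14 points |
| 50% | 0.50 + 0.50 × 0.20 = 60% | 0.50 + 0.50 × 0.40 = 70% | 10 points |
| 70% | 0.70 + 0.30 × 0.20 = 76% | 0.70 + 0.30 × 0.40 = 82% | 6 points |

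The effect on power was checked with 36 per arm, two-sided 0.05 and an assumed later risk of 10% v 40%. The normal approximation for two proportions is shown, with exact Fisher power in brackets:

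| p1 | Six-month incidence | Power |
|---|---|---|
| 0% | 10% v 40% | 85% (80%) |
| 20% | 28% v 52% | 55% (44%) |
| 40% | 46% v 64% | 33% (24%) |
| 60% | 64% v 76% | 20% (14%) |

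In calendar time the shared period is about 30 of 180 days, or 17% of follow-up. The loss depends on p1, not on that share.

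**The case against.** The strongest reply is that the data are not lost and that the six-month comparison is legitimate. Urinary protein/creatinine ratio is listed among objectives timed from the start of everolimus. The lipid profile is monitored, and the Safety objectives also ask for reasons for dose interruption and adjustment. The SAP's Mann-Whitney test could compare laboratory values without any grade. The tolerability aim covers the regimens as a whole, so counting from transplant by randomised arm answers a real question. The documents do not name Group 2 v Group 1 as the safety contrast. All the rates above are assumed, and any-event incidence is the summary most exposed to dilution.

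Much of this stands. It limits the point to definition and tabulation, but does not remove it: no baseline, threshold or window is given for summarising those measurements.

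A reader might infer stronger claims, which the documents do not support:

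- *Everolimus toxicity is masked.* The text does not say before transplant, and no laboratory trajectories are given. Masking is possible under one reading but not shown.
- *Severe laboratory toxicity will be reported as mild.* The scale is stated for clinical events, so laboratory events are ungraded rather than wrongly graded.
- *Any symptomatic event in an inpatient can be called severe.* That overlooks the requirement that the event be incapacitating.
- *The six-month comparison is biased.* It is a valid whole-regimen comparison that is less sensitive to what everolimus adds.

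**Conclusion.** The point holds as a gap in definition and analysis. The adverse event reference is ambiguous, and neither available reading suits a drug added to one arm at about POD 30. The laboratory effects that the protocol sets out to evaluate have no severity criteria. No safety window starts at everolimus introduction, although the protocol already measures eGFR change from that point.

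The size of the dilution cannot be fixed from the documents. The Group 2 v Group 1 difference in any-event incidence keeps a fraction (1 - p1): 70%, 50% or 30% of it for p1 of 30%, 50% or 70%, and all of it for a toxicity that does not occur before POD 30. This rests on equal p1 in the two groups, on later risk not depending on an early event, and on assumed rates. The grading and reference gaps do not depend on those assumptions. The change should be made, because it is cheap and the everolimus safety contrast is hard to interpret without it.

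**What to change.** 1. **Reference.** In the Adverse Events section, define an event starting after POD 30 against the last value or condition at or before POD 30, in all three arms. In Group 2 that value must also precede the first everolimus dose. The everolimus timing must be reconciled first: the Drug Therapy lists have it added by POD 30, while the Investigational Treatment section has it introduced no earlier than 1 month after transplant.
2. **Grading.** Grade laboratory events by numeric criteria from a named published toxicity scale, applied to measured values. Keep the 3-point scale for symptoms. Confirm that platelets, white cells, hemoglobin, lipids and urinary protein are scheduled at and after POD 30, because the text sets out no visit schedule for them.
3. **Tables.** In the SAP, tabulate adverse events, infections and laboratory toxicity by randomised arm for two periods: transplant to POD 30, and POD 31 to month 6. The second-period denominator is patients alive and in follow-up at POD 30. Name Group 2 v Group 1 in the second period as the everolimus safety contrast, and keep the six-month total as the whole-regimen comparison.

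The cost is protocol and SAP wording and one extra set of tables. More laboratory events will be reported in every arm.

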### **Criteria for Early Withdrawal**

All patients have the right to discontinue the clinical trial at any time for any reason. However, all patients who have discontinued the trial will be followed for the entire 6 months post-transplant.

### **Collection of Data**

Data on each enrolled patient will be kept on site at UCLA in a secured site. Subject privacy and confidentiality will be maintained. A computer generated database (coded encrypted data with access code) will maintain the files on each patient enrolled.

### **Study Completion**

At study completion, results will be targeted towards the American Society of Transplantation and/or the journal American Journal of Transplantation, Liver Transplantation, or Transplantation

### **Institutional Review Board/Ethics Committee**

This protocol and any other material provided to the patient will be provided to the Institutional Review Board/Ethics Committee. Approval from the IRB/EC must be obtained before initiation of this clinical trial and should be documented in writing. Any modifications made to the protocol must be submitted to the Committee.

### **Estimated Budget**

~\$3,500/patient

Official Title:

A Study in Adults on Pre-LT Dialysis With Basiliximab, Delayed Tacrolimus (TAC), Mycophenolate (MMF), and Steroids (Group 1) vs. Basiliximab, Delayed TAC, MMF, Steroids, With Everolimus 30 Days Post-LT (Group 2) vs. TAC, MMF, and Steroids (Group 3)

NCT Number:

NCT04104438

Document Date:

September 3, 2020

Statistical Analysis

Continuous variables were expressed as median (range) and were compared using the Mann-Whitney U test. Categorical variables were expressed as a numerical percentage and compared by the Chi-square test or the Fishers Exact Test. Survival curves were generated by the Kaplan-Meier method, and differences in survival rates were analyzed using the Log-Rank test. All tests were two-sided, and the significance level was $p<0.05$. All analyses were performed using IBM® SPSS® Statistics version 26 (IBM Corporation, Armonk, NY).

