## **PRIMARY ENDPOINTS**

- Assessment of the nephroprotective effects of everolimus in combination with simulect, or simulect alone following OLT at months 2, 3, 4, 5 and 6.

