## **SECONDARY ENDPOINTS**

- Mean serum creatinine, eGFR (MDRD) at weeks 1, 2, 4, 8, 12, 16, 20 and 24
- 1, 3 month and 6 month cumulative incidence of acute allograft rejection episodes, steroid resistant rejection episodes, dialysis requirements
- Incidence of death and/or graft failure at 6 months
- Tolerability and side effect profile of the combination drug therapies
- Incidence of infectious complications
- Time to first episode of acute rejection
- Refractory rejection episodes (requiring immunosuppression beyond T cell depletion)
- Rejection episodes per subjects
- Number of subjects requiring full-dose calcineurin inhibitor rescue therapy
- Monitor CD25 cell count for 3 months
- Economic analysis to determine cost-effectiveness of induction therapy with IL-2 monoclonal antibody
- Economic analysis to determine cost-effectiveness of delayed therapy with mTOR

**A three arm, single center, randomized, prospective, pilot trial of induction and maintenance immunosuppression with basiliximab, delayed dose tacrolimus plus mycophenolate mofetil, and SOC corticosteroids versus immunosuppression with basiliximab, delayed dose tacrolimus plus mycophenolate mofetil, and SOC corticosteroids with delayed addition of everolimus and mycophenolate minimization versus standard dose tacrolimus and mycophenolate mofetil plus corticosteroids in patients undergoing orthotopic liver transplantation (OLT) with concomitant renal dysfunction**

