## **Efficacy objectives at 1, 2, 3, and 5 months after start of everolimus**

To assess:

- Rate of composite efficacy failure of treated biopsy proven acute rejection (tBPAR), graft loss (GL) or death (D).
- Time to event and severity of tBPAR.
- Incidence and severity of all acute rejection.

To evaluate:

- Renal function over time assessed by mean change in eGFR by the Cockcroft and Gault (MDRD) from the start of everolimus.
- Urinary protein/creatinine ratio at various time points
- Incidence of and time to renal replacement therapy.

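### The creatinine and eGFR endpoints are means and mean change over repeated visits, but the SAP offers only medians with a Mann-Whitney test: no mean-difference estimate or interval, no stated baseline adjustment, no repeated-measures method

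*SAP*

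**What the plan says.** The protocol's Statistical analysis section is still to be determined, so the one-paragraph SAP is the only statistical plan. For continuous data it says: "Continuous variables were expressed as median (range) and were compared using the Mann-Whitney U test". For the rest it says "Categorical variables were expressed as a numerical percentage and compared by the Chi-square test or the Fishers Exact Test" and "Survival curves were generated by the Kaplan-Meier method, and differences in survival rates were analyzed using the Log-Rank test". Tests are two-sided at 0.05.

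The protocol words its continuous renal outcomes as follows:
- Synopsis, Secondary Endpoints: "Mean serum creatinine, eGFR (MDRD) at weeks 1, 2, 4, 8, 12, 16, 20 and 24".
- Purpose, Secondary Objectives: "To determine the mean serum creatinine concentration and eGFR: Cockcroft and Gault (MDRD", at the same eight weeks.
- Efficacy objectives after start of everolimus: "Renal function over time assessed by mean change in eGFR", counted from the start of that drug.
- Introduction: eGFR is also named as part of the primary objective.

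Two other statements bear on the scope. The Primary Endpoints entry concerns nephroprotection with everolimus plus simulect or with "simulect alone following OLT at months 2, 3, 4, 5 and 6"; it gives repeated visits but no variable or summary measure. The Primary Objectives entry under Purpose uses dialysis independence and the time to reach it.

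**The concern.** A Mann-Whitney p-value with medians and ranges does not answer a question posed as a mean or a mean change. It gives a reader no size of renal benefit and no interval around it. In a study that calls itself a pilot, that estimate is the most useful thing the renal data can supply.

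The SAP also names no baseline covariate and does not say how 5 to 8 measurements on the same patient are to be combined. With arms of 36, 36 and 18, a useful gain in precision may go unused. If the test is simply repeated by visit and by pair of arms, the result is a list of p-values with no designated main one.

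**Working it through.** **Inputs from the documents.** 90 patients randomised 2:2:1 (Patient Population): 90 × 2/5 = 36, 36, and 90 × 1/5 = 18. Two-sided 0.05 (SAP). Eight creatinine/eGFR visits, and five monthly visits for the primary endpoint. There is no effect size, SD, correlation, dropout rate or power statement, so there is no figure of the plan's own to reproduce.

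**Assumed.** Difference 0.6 SD; correlation r between baseline and follow-up of 0.3, 0.5 or 0.7; normal data; no dropout.

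**1. Endpoint against method.**

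| Outcome | Stated measure | SAP method | Match |
|---|---|---|---|
| Creatinine, eGFR at 8 visits | Mean | Median (range), Mann-Whitney | No |
| eGFR from start of everolimus | Mean change over time | Median (range), Mann-Whitney | No |
| Dialysis independence | Proportion | Chi-square or Fisher | Yes, in type |
| Time to dialysis independence | Time to event | Kaplan-Meier, log-rank | Yes, in type |

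**2. Does the mismatch matter?** Take two lognormal groups, both with median 60, and log-SDs of 0.3 and 0.6. The means are 60 × exp(0.3²/2) = 62.8 and 60 × exp(0.6²/2) = 71.8, a difference of about 9. The chance that a value from one group falls below a value from the other is 0.50, so the rank test has nothing to detect. The two medians in the table would be equal.

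**3. Precision.** Baseline adjustment multiplies the variance by 1 − r²: 0.91, 0.75 or 0.51. In SD units the standard error is √(1/36 + 1/36) = 0.236 for 36 v 36 and √(1/36 + 1/18) = 0.289 for 36 v 18. Power ≈ Φ(0.6/(SE × s) − 1.96), with s = √(π/3) = 1.023 for Mann-Whitney and s = √(1 − r²) for the adjusted mean.

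| | Mann-Whitney | Adjusted, r = 0.3 | r = 0.5 | r = 0.7 |
|---|---|---|---|---|
| 36 v 36, formula | 70% | 76% | 84% | 95% |
| 36 v 36, simulated | about 69% | about 75% | about 83% | about 94% |
| 36 v 18, formula | 53% | 59% | 67% | 83% |
| 36 v 18, simulated | about 50% | about 56% | about 64% | about 80% |
| Detectable at 80% power, 36 v 36 | 0.68 SD | 0.63 SD | 0.57 SD | 0.47 SD |
| Detectable at 80% power, 36 v 18 | 0.83 SD | 0.77 SD | 0.70 SD | 0.58 SD |

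**4. Where the gain fails.** At r = 0 simulated power is 69% (Mann-Whitney) v 70% (adjusted) in 36 v 36, and 50% v 52% in 36 v 18. With lognormal data (assumed log-SD 0.8, 0.6 SD difference on the log scale) analysed untransformed at r = 0.3, Mann-Whitney does better in 36 v 36: 69% v 60%. On the log scale that example is normal again, and the table in step 3 applies.

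**5. If changes were ranked.** With s = 1.023 × √(2(1 − r)), power at r = 0.3, 0.5, 0.7 is 56%, 70%, 90% in 36 v 36 and 40%, 53%, 75% in 36 v 18. This is below the adjusted analysis at every r, and below ranking raw values at r = 0.3.

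**6. Repeated testing.** Five visits × three pairs = 15 tests at 0.05. The simulated chance of at least one false positive is 40%, 32% or 26% at visit correlations of 0.5, 0.7 or 0.85. This reflects the number of tests; fifteen model contrasts would raise the same issue.

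**The case against.** The strongest defence is that Mann-Whitney with medians is a valid, robust choice for small and possibly skewed groups, and that the Primary Objectives entry is about dialysis, which the SAP's other tests fit. Both statements are true. They limit the point to creatinine and eGFR, and they mean that the fault lies in the missing estimate and not in an invalid test.

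A reader might infer several stronger things that the documents do not support:
- *Every renal endpoint is mismatched.* The dialysis outcomes are not, and the Primary Endpoints entry has no measure to mismatch.
- *The SAP throws baseline data away.* It is silent on whether raw values or changes are ranked, and a rank test on change would use baseline. What can be said is that no adjustment is stated. Step 5 shows that the unstated choice moves power materially.
- *Extra precision is free.* Eligible patients may have been on dialysis for up to 45 days, and the SAP title describes adults on dialysis before transplant. Creatinine measured then partly reflects the dialysis, so r could be below 0.3, and skewness could reverse the gain.
- *The 26% to 40% error rate condemns Mann-Whitney.* It is a multiplicity matter, and visit-by-visit testing is itself only a likely reading of the SAP. Naming one main time point removes it under either method.

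A baseline-adjusted model also brings difficulties of its own: what counts as baseline, and what to do with eGFR on dialysis or after death. Those stand, and the remedy has to deal with them.

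**Conclusion.** The point holds for the creatinine and eGFR endpoints. The plan as written cannot deliver the means and mean changes that the protocol promises, and it leaves baseline adjustment and repeated visits unaddressed. That conclusion comes from the two texts and needs no assumption.

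The size of the precision gain does need assumptions. With a 0.6 SD difference and normal data it runs from about 6 percentage points of power at r = 0.3 to 25 in 36 v 36 (94 − 69) and 30 in 36 v 18 (80 − 50) at r = 0.7. It is close to nothing at r = 0 and can be negative for untransformed, strongly skewed data. The change should be made mainly for the sake of the estimate and its interval; the likely gain in power is secondary. It should be made, but it does not invalidate the trial.

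**What to change.** **Main analysis.** Analyse eGFR and creatinine, on the log scale if skewed, with a repeated-measures model containing arm, visit, arm by visit, the pre-transplant value, and pre-transplant dialysis status or duration. Report differences between arms with 95% confidence intervals. Name one main time point before analysis, for example month 6; the protocol ranks no month, so this is the sponsor's choice.

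**Change from the start of everolimus.** Groups 1 and 3 have no such start, and weeks 1, 2 and 4 precede it, so this cannot share the main model's baseline. Fit a separate model for Group 2 v Group 1. Take as baseline the last value before a common reference day (about POD 30), and use later visits only. State that this comparison is limited to patients alive with a value at that day.

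**Rules and sensitivity.** State how eGFR on dialysis and after death is handled in each model. Keep a rank analysis as sensitivity, with dialysis or death ranked worst and preferably adjusted for baseline.

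**Cost.** SAP text and modest analysis work; no new patients, visits or measurements. The handling rules need some thought, so this is more than a change of test name. The downside is reliance on a model, which the rank analysis guards against. If results are already known, the model should be labelled post hoc.

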## **PATIENT POPULATION**

In a 2:2:1 fashion, 90 subjects (group 1: n=36; group 2: n=36; group 3: n=18) will be randomized at UCLA Medical Center. Each subject will be followed for 6 months post-transplant.

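### The cost-effectiveness objectives have no usable analysis: by default per-patient cost falls to median and Mann-Whitney, which cannot give a mean cost difference or set cost against effect.

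*SAP*

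**What the plan says.** The protocol synopsis, under Secondary Endpoints, lists "Economic analysis to determine cost-effectiveness of induction therapy with IL-2 monoclonal antibody" and "Economic analysis to determine cost-effectiveness of delayed therapy with mTOR". The Secondary Objectives section repeats both items, the second as "Economic analysis to determine cost-effectiveness of delayed therapy with everolimus". Neither place names the cost items, the effect measure, the perspective, the period over which costs count, or the groups to be compared.

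The protocol's Statistical analysis section contains only TBD. The SAP is a single paragraph. For continuous data it says "Continuous variables were expressed as median (range) and were compared using the Mann-Whitney U test"; categorical data get chi-square or Fisher's exact test, and survival gets Kaplan-Meier and log-rank, all two-sided at 5%. It has no exception or separate section for costs. Neither document mentions mean cost, incremental cost, a cost-effectiveness ratio, net benefit or resampling.

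On size and duration, the synopsis says "In a 2:2:1 fashion, 90 subjects (group 1: n=36; group 2: n=36; group 3: n=18) will be randomized at UCLA Medical Center" and "Each subject will be followed for 6 months post-transplant".

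**The concern.** A cost-effectiveness statement sets a difference in mean cost per patient against a difference in mean effect. The mean matters because mean cost times the number of patients is the total paid; the median has no such property. Mann-Whitney tests whether a patient drawn from one arm tends to cost more than a patient drawn from the other. It gives no estimate of the mean difference, and neither its p-value nor a difference in medians can be combined with an effect difference.

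This trial has the structure in which ranks and means can part company. Everolimus is added for every Group 2 patient from about one month. Any offsetting saving would come from the minority who avoid dialysis or a rejection admission. The median registers the drug cost carried by all and largely misses the saving in a few. What is at stake is two stated objectives left without an answer, and a p-value on cost that could be over-read in the wrong direction.

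**Working it through.** **What the documents supply.** Arm sizes are 36, 36 and 18 (90 split 2:2:1 gives 90 × 2/5 = 36 twice and 90 × 1/5 = 18), follow-up is 6 months, and tests are two-sided at 5%. There is no stated cost, event rate or power figure to reproduce. The only money figure is the estimated study budget of about $3,500 per patient, which is not a cost of care. Everything below about costs is therefore assumed.

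**Step 1: what the rule can return.** Applied to cost, it gives a median and range per arm and a p-value. An incremental cost-effectiveness ratio needs (mean cost A − mean cost B) / (mean effect A − mean effect B). Net monetary benefit needs λ × effect difference − mean cost difference, with λ the value placed on one unit of effect. The rule supplies neither the cost term nor any link between a patient's cost and that patient's effect. This holds whatever the costs are.

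**Step 2: can the direction be wrong?** Assumed model, in thousands of dollars per patient:
- other costs: lognormal, coefficient of variation 0.5, mean 10, 20, 40, 100 or 150;
- drug: 5 or 10, added to every Group 2 patient;
- costly event: in 10% of Group 2 and 25% of the comparator, gamma with shape 4.

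Equal means require event cost = drug / (0.25 − 0.10). For drug 10 this is 66.7. The comparator's event cost averages 0.25 × 66.7 = 16.7, and Group 2's event plus drug cost averages 0.10 × 66.7 + 10 = 16.7. Raising the event cost by half, to 100, gives 0.25 × 100 = 25 against 0.10 × 100 + 10 = 20, so Group 2 is truly cheaper by 5 (by 2.5 for drug 5).

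Percentage of 6,000 simulated trials in which Mann-Whitney at two-sided 5% declares Group 2 dearer (nominal 2.5%):

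| Drug | Other costs | Equal means, 36 v 36 | Group 2 cheaper, 36 v 36 | Equal means, 36 v 18 |
|---|---|---|---|---|
| 5 | 10 | 50.5 | 48.7 | 37.6 |
| 5 | 20 | 12.4 | 10.5 | 11.4 |
| 5 | 40 | 4.1 | 2.7 | 4.7 |
| 5 | 100 | 2.6 | 1.8 | 2.9 |
| 5 | 150 | 2.8 | 1.7 | 2.5 |
| 10 | 10 | 89.0 | 88.6 | 72.3 |
| 10 | 20 | 50.5 | 47.9 | 37.2 |
| 10 | 40 | 12.9 | 10.0 | 11.9 |
| 10 | 100 | 3.2 | 1.7 | 3.5 |
| 10 | 150 | 2.4 | 1.8 | 2.6 |

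**Step 3: a second model.** Routine cost has mean 1 and log-SD 0.3, events occur in 5% v 15%, and true means are equal. Group 2 is called dearer at 36 v 36 in about 7%, 34% and 72% of trials for a drug cost of 10%, 20% and 30% of routine cost. When the arms are lognormal and differ only by a scale factor there is no excess: 2.6% at equal means and 0.8% when everolimus is 10% cheaper. What drives the error is drug cost relative to the spread of the other costs.

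**Step 4: a mean-based comparison in the first model.** At equal means Welch's test rejects in 4.6% to 5.3% of trials at 36 v 36, but in up to 7.0% at 36 v 18, mostly in the dearer direction (up to 6.4% against a nominal 2.5%). With strongly unequal lognormal skew the dearer call reaches 6% to 15%.

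**The case against.** The strongest objection is that the SAP never assigns costs to Mann-Whitney. Its paragraph is generic, the objectives ask for an economic analysis, and the plainer description is that none is specified. This stands in part: the rule reaches cost only by default, as the one rule for a continuous variable. A reader might cite the SAP's closing sentence about all analyses as proof that costs are included, but that sentence names the software and says nothing about which test applies. The repair is the same on either description.

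Second, the large error rates need other costs of about the same order as the drug cost. Follow-up runs from transplant and basiliximab is given around surgery, so a count from transplant to month 6 includes the transplant admission. With other costs of 100 to 150 the excess disappears. This stands. It limits the wrong-direction argument but leaves Step 1 untouched.

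Third, a reader might infer that basiliximab would be wrongly judged dearer in the same way. The ranks-versus-means argument applies to any cost, but the simulations model a drug given throughout Group 2, not a two-dose induction, so no error rate is shown for that contrast.

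Fourth, comparing means is not clean with 18 controls. This stands, and is why the fix asks for intervals and an exploratory label.

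**Conclusion.** The point holds in this form: two secondary objectives ask about cost-effectiveness, and the only rule that could be applied to cost cannot answer them. That conclusion rests on the text alone.

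The further point, that the rule can call everolimus dearer at equal or lower mean cost, is true as a possibility. Its size runs from no excess to over 70% (89% at 36 v 36 and 72% at 36 v 18 when drug and other costs are equal), entirely under assumed costs. A reader might infer that the trial is likely to reach the wrong economic conclusion. The documents do not support that: they give no costs, they do not say when cost counting starts, and the rule produces no cost-effectiveness estimate that could be wrong.

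Severity is minor, since these are secondary objectives of a trial described as a pilot.

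**What to change.** Add to the SAP:

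> Costs are exempt from the median and Mann-Whitney rule. For each named contrast we will report the difference in arithmetic mean cost per randomised patient, with the start and end of cost counting stated, and a bootstrap 95% confidence interval. Each patient's cost and a named effect measure will be resampled together within arm, and net monetary benefit or the incremental cost-effectiveness ratio will be reported with its interval. No conclusion on cost-effectiveness will be drawn from a p-value on median cost. Contrasts with the control arm are exploratory.

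The authors need to fill in the contrast for each objective, the cost perspective, the counting period and the effect measure. The counting period matters most, because it decides whether the transplant admission is included.

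The cost is a few sentences and a short resampling run, with no data beyond what the objectives already require. The protocol already says that patients who discontinue are followed for the full six months, which helps keep costs complete. The downside is wide intervals. With 18 controls, mean-based intervals for skewed costs may also under-cover somewhat, hence the exploratory label.
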